8.0 Study Calendar

Phone Screen (Expected duration 10-15 minutes)

-----Variable time to Visit 1; Up to 6 months-----

Visit 1 (Expected duration 3-4 hours)

Procedures may be split into multiple visits

1. **Informed Consent/Accent***
2. **K-SADS-PL***
3. **Parent/Child surveys***
4. **IQ test**
5. **VR Practice & Avatar Creation**
6. **Mock Scanner**

***May be conducted remotely**

-----Up to 6 weeks from K-SADS-PL until Visit 2-----

Visit 2 (Expected duration 2 hours)

1. **MRI Scan**

-----Up to 2 weeks until Visit 3-----

Visit 3 (Expected duration 2-3 hours)

- 1. VR Scenarios & Assessments**
- 2. VR Scenarios (Assigned Perspective Condition) & Assessments**
- 3. MRI Scan**

	Visit 1	Visit 2	Visit 3
Parent & Child: K-SADS Clinical Interview	X		
Parent: Demographics; Outburst Monitoring Scale; NIH Toolbox Emotion Battery; Media Exposure Questionnaire; VR Experience Survey; Family Environment Scale; Sleep Disturbances Scale for Children	X		
Child: Interpersonal Reactivity Index; NIH Toolbox measures; Inventory of Callous-Unemotional Traits; Media Exposure Questionnaire; VR Experience Survey; Video Game Motivations and Desires Scale; Impulsive Behavior Scale	X		
Parent & Child: MRI Screening Form	X	X	X
Child: VR Practice & Avatar Creation	X		
Child: Simulation Sickness Questionnaire	X		X
Child: Mock Scan	X		
Child: MRI Scan		X	X
Child: VR task & assessments (VR Perspective Taking Scale; Acknowledgement of Other Perspective Scale; Post-scenario Survey; Mood state; VR Usability & Environmental Presence)			X

9.0 Reportable Events

All serious adverse events (SAEs) and Unanticipated Problems Involving Risks to Subjects or Others (UPIRTSO) will be immediately reported to the Indiana University Institutional Review Board (IRB) within 5 working days; other adverse events or protocol deviations will be reported to the IRB based on IRB guidelines (typically reported at the time of renewal). We will also

report to the NIMH program officer within 10 working days. An example of a rare but serious adverse event is injury from metal objects in the proximity of the MRI scanner. Mild, temporary VR sickness (e.g., nausea) will be considered an adverse event but not a serious adverse event.

Any adverse events (serious or not), as well as the progress of the study will be reviewed and discussed in detail at the meetings of our DSMB. Non-serious adverse events or protocol deviations will be reported to the IRB based on IRB guidelines (typically reported at the time of renewal).

For all AEs and SAEs deemed unexpected and/or unrelated to the study, a summary will be submitted to the NIMH PO with the annual progress report. Protocol violations will also be included in this annual progress report. Temporary suspension of the study will be reported to NIMH within three working days, along with a statement of the reason(s) for the action.

10.0 Data Safety Monitoring

PI [name], in consultation with co-Investigators [name] and [name], is responsible for data and safety monitoring and ensuring that the protocol is being properly followed, with independent oversight also provided by a local Data and Safety Monitoring Board (DSMB). Data quality, subject recruitment, accrual, retention, outcome and adverse event (AE) data, procedures designed to protect the privacy of subjects, and subject satisfaction will be monitored. Any unanticipated problems encountered or observed by research staff will be promptly reported to [name]. If [name] will be unavailable for contact for an extended period while study procedures are ongoing, he will designate a co-investigator to be the primary contact for research staff should such problems arise.

Co-investigators [name] and [name] will help [name] distinguish serious from non-serious adverse events, as well as relatedness to study participation. SAE's will be graded based on the Mild-Moderate-Severe grading scale. The scale is as follows: Mild - no limitation of usual activities, Moderate - some limitation of usual activities, or Severe - inability to carry out usual activities.

Any adverse events (serious or not), as well as the progress of the study will be reviewed and discussed in detail at the meetings of our ad hoc DSMB. These meetings will occur at least once every six months. Additional meetings will be scheduled "as needed." This board consists of experts in child psychology, information technology, clinical trials, and biostatistics. This DSMB is currently headed by [name] (Professor of Physical Medicine & Rehabilitation).

A report is generated on this study from each meeting, which will be shared with the NIMH program staff. The reports contain a summary of enrolled, discontinued, and recruited subjects, a list of any adverse events and details reviewed by the DSMB. Any findings, concerns or recommendations of the DSMB, along with an action plan for how to implement those recommendations, will be provided.

[name] lab team (research assistant, research coordinator, postdoctoral fellow, volunteer student researchers) will meet weekly discuss study progress and issues, and all study

personnel (PI, co-investigators, research staff) will meet semi-annually to review data, number of subjects, responses observed, and any concerns not otherwise addressed (i.e., other than adverse events or protocol deviations). At weekly lab meetings, a different co-investigator will be involved once a month, so each co-investigator will be present at least once every 3-4 months, in addition to semi-annual meetings.

Each meeting will have specific time dedicated to any issues in study data that pertain to safety of subjects. Any safety issue that requires temporary suspension of the study will be reported to the IRB and NIMH within three working days, along with a statement of the reason(s) for the action. In addition, [name] and research staff will review study enrollment at weekly lab meetings and compare present status to enrollment targets. Data will be presented on enrollment numbers, screen fails, and withdrawn subjects, as well as race/ethnicity and sex of subjects. If necessary, we will modify recruitment efforts in order to maintain ability to reach target enrollment for race, ethnicity, and sex.

All study staff, including the PI, will complete (and as needed, renew) required training regarding the protection of human subjects, informed consent procedures, and confidentiality. This training includes completion of CITI (Social/Behavioral/Educational Researchers) and Good Clinical Practice training. The trial will not begin until researchers have completed the Good Clinical Practice training.

11.0 Study Withdrawal/Discontinuation

A child participant or their parent may withdraw from the study at any time by letting the research team know they wish to discontinue their participation. The participant(s) will be paid for their time completed in the study.

Participants will be precluded from continuing the intervention if they report adverse health consequences from using virtual reality equipment during practice or intervention. In addition, inability to complete the MRI scan, including claustrophobia or an unforeseen health consequence, will also halt a subject's participation.

If a worsening of DBD symptoms is identified via voluntary report or visit assessments, the family will be queried to determine the nature of symptoms, including relationship and proximity to study procedures. [name] and clinical psychologists on the team will review these data, and if a worsening of symptoms is judged to be significant and likely related to study participation, the subject will be discontinued from participation. Additionally, depending on the severity of symptoms, the subject may be offered or referred for further evaluation of symptoms; the urgency of this evaluation will depend on the nature and severity of symptoms but may range from a standard outpatient visit to an urgent/emergent evaluation.

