3.0 Outcome Measures

Primary Outcome Measure: VR Perspective Taking Scale

This scale measures the degree to which participants understand the perspective of their virtual counterpart. It will be completed after each VR scenario, both pre- and post-intervention. Each participant's change score will be as Post-treatment (Endpoint; following all VR) vs. Pre-treatment (Baseline; after first scenario). The Cohen's d effect size will be calculated using the difference in mean change scores between treatment and control conditions (e.g., $[\text{Mean}_{\text{Enriched Post-Pre}} - \text{Mean}_{\text{Control Post-Pre}}] / \text{SD}_{\text{pooled}}$), resulting in an effect size measurements for both scales with each treatment condition.

Primary Outcome Measure: Acknowledgement of Other Perspective Scale

This scale allows participants to rate the relative importance of the virtual counterpart's perspective with a scenario-specific question. It will be completed after each VR scenario, both pre- and post-intervention. Each participant's change score will be as Post-treatment (Endpoint; following all VR) vs. Pre-treatment (Baseline; after first scenario). The Cohen's d effect size will be calculated using the difference in mean change scores between treatment and control conditions (e.g., $[\text{Mean}_{\text{Enriched Post-Pre}} - \text{Mean}_{\text{Control Post-Pre}}] / \text{SD}_{\text{pooled}}$), resulting in an effect size measurements for both scales with each treatment condition.

Primary Outcome Measure: Neural response to Self vs. Other Pain

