After the MRI, the subject will be presented with a series of images. They will then determine which of the images they saw while completing the tasks in the MRI. This task measures how well subjects were attending to stimuli during the brain scan.

Visit 3

Participants will take part in the VR task with the Oculus Quest VR headset. We will fit the headgear to the child and ensure that it is comfortable. Subjects will remain seated while interacting with the virtual world and use hand-held controls to move or control objects. Subjects can turn their head to look in any direction in the virtual world. Using state-of-the-art 'Oculus Touch' hand-held controllers that react to hand movements, the user will be able to move and interact with virtual objects and characters. Headphones play auditory stimuli.

Children will first explore the virtual cafeteria for three minutes to allow them to understand hand controls and become acquainted with the environment before starting the task scenarios. They may ask questions and talk with investigators during this time, who will ensure that subjects are able to use controls and move around in the environment properly.

The virtual environment is a school cafeteria setting. Following practice, participants will take part in three scenarios in the school cafeteria. Each scenario will last up to two minutes. In two scenarios, after the subject hears the school bell ring, the goal is to place trash on their cafeteria tray and take the tray to the trash. In a third scenario, the subject is directed to clean up the mess at their table. Once the task is complete, the scenario will be complete. In each scenario, virtual characters will populate the environment to make it more realistic, including some characters (students) who will also be returning their trays. However, the social environments will differ, and each scenario includes a virtual counterpart that interferes with the goal.

After each scenario, children will remove the headset and complete questions via electronic tablet. First, they will complete our **VR Perspective Taking Scale**, which assesses how well they understand the virtual counterpart's perspective. Next, they will complete a question for the **Acknowledgement of Other Perspective Scale**, which reflects the relative importance given to the perspective of the participant and the virtual counterpart.

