They will also complete a **Post-scenario Survey** regarding how they interpreted the intentions of the virtual counterpart (Were any of the characters trying to be nice to you? Were any of the characters trying to be mean to you?) and real-life responses (Would you be mad if this happened in real life? Would you try to hit other characters if this happened in real life?). Responses will be provided on a continuous sliding scale from 0 to 100 with labeled endpoints. We will also quickly assess current mood state (happy, sad, stressed, frustrated, calm) on sliding scales and complete the **Simulation Sickness Questionnaire** and a **VR Usability Survey**.

Following completion of each scenario, subjects will then experience the scenario again. Each subject will be randomly assigned to the (a) Alternate Perspective or (b) Control Perspective. In the Alternate Perspective condition, participants will experience the scenarios again from the virtual counterpart's perspective within the VR system. The Control Perspective will repeat the initial interaction from the same perspective. After each scenario, participants will answer questions identical to those after initial scenarios: the **VR Perspective Taking Scale** and the **Acknowledgement of Other Perspective Scale**, as well as questions about character intent, real-life responses, mood, the **Simulation Sickness Questionnaire**, and **VR Usability**.

If errors with the VR technology are observed, subjects may restart the scenarios and subsequent surveys.

Parents will also once again complete the Indiana Institute of Biomedical Imaging Sciences (IIBIS) **MRI Safety Screening Form** and the **Medication Log**.

Participants will be instructed about the MRI task and will briefly practice again. Participants will then undergo an MRI scan for about 1 hour. This scan may not be performed if the previous scan (at Visit 2) was not completed successfully. This scanning session will be identical to Visit 2, including an anatomical scan and functional scans in which participants will see images of painful and non-painful actions, under conditions where they are told to imagine scenes happening to themselves or the virtual counterpart, as well as the emotional face task.

After the scan, participants will be presented with images and asked to identify which ones they remember from the MRI scan.

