12.0 Statistical Considerations

We will enroll 95 children in order to target 40 completers ($n = 20/\text{group}$, allowing for 15-20% screen fail and 15-20% attrition). Attrition (apart from screen fails) will occur between the two scanning visits, which are only one week apart and are expected to be due to noncompliance or in-scanner subject motion that renders data unusable. Attrition rates are not expected to

change from year to year, as subjects will remain active only from the time of screening to Visit 3 (up to 8 weeks).

In similar research, pre/post correlations of 0.72 and 0.89 were found for measures of Theory of Mind (closely related to social perspective taking) in a VR intervention for social cognition training.⁵⁰ In research by co-I [name] involving a multi-session skill-building intervention,⁵¹ pre/post scores had a correlation of 0.69 on the Perspective Taking subscale of the Interpersonal Reactivity Index. Here, we use a more conservative estimate for a pre/post correlation of social perspective taking of 0.6. With 20 subjects per group and assuming an ANCOVA model (specified below) is used with a pre/post correlation for social perspective taking of 0.6 an effect size of 0.73 (observed for the meanness rating in the preliminary study) can be detected between two groups with 80% power using a two-sided two-sample t-test with alpha level of 0.05.

For each primary outcome measure, a separate linear mixed model will be employed to determine predictors of post-treatment scores, with pre-treatment scores, condition, time, group, and a time-by-condition interaction term as regressors. Time-by-condition is a regressor to account for potential improvements in perspective taking with treatment (since there are two conflict scenarios presented). From this model, using appropriate contrast statements we can both test for the primary endpoint (change at end of Scenario 3) and examine trends over time between the three groups. We will also conduct with fMRI data a 2x3 (pain perspective condition by group) within-subjects ANOVA on data from each ROI.

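### Section 11 halts a child who cannot complete the MRI; if that happens at Visit 2, both VR primary scales are lost although neither needs a scan

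*Combined protocol and SAP*

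**What the plan says.** Section 11.0 (Study Withdrawal/Discontinuation) states that "inability to complete the MRI scan, including claustrophobia or an unforeseen health consequence, will also halt" the child's participation. It does not separate the Visit 2 scan from the Visit 3 scan, and it does not provide for stopping the scans alone.

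Section 7.0, under Visit 3, says of the second scan: "This scan may not be performed if the previous scan (at Visit 2) was not completed successfully".

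Section 3.0 names three primary outcomes: the VR Perspective Taking Scale, the Acknowledgement of Other Perspective Scale, and the fMRI response to self versus other pain. Of each VR scale it says "It will be completed after each VR scenario, both pre- and post-intervention". Section 7.0 gives the method: "After each scenario, children will remove the headset and complete questions via electronic tablet". The Study Calendar (8.0) puts the only scan of Visit 2 ahead of all VR scenarios. Within Visit 3 it lists "VR Scenarios (Assigned Perspective Condition) & Assessments" before the MRI.

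Section 12.0 says "For each primary outcome measure, a separate linear mixed model will be employed". On numbers it says "We will enroll 95 children in order to target 40 completers", allowing 15-20% for screen failure and 15-20% for attrition. The attrition is "expected to be due to noncompliance or in-scanner subject motion that renders data unusable".

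**The concern.** The discontinuation rule is tied to one outcome but removes data on all three. A child who becomes claustrophobic in the scanner at Visit 2 cannot supply fMRI data, but nothing in the plan makes that child unable to sit through short VR scenarios and answer questions on a tablet. Followed literally, Section 11 ends participation before any VR rating exists, so the pre and post values of both VR scales are lost together.

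Section 7.0 makes this harder to apply. Its sentence about omitting the Visit 3 scan is useful only if some children with an unsuccessful Visit 2 scan still attend Visit 3. The plan never says which children stop and which go on without a scan.

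At stake are a few VR ratings in a trial that targets 20 completers per arm, and a VR sample limited, without need, to children who tolerate scanning.

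**Working it through.** **Order of events.** Three facts from Sections 3.0, 7.0 and 8.0 decide what is lost:

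| Event | Visit | VR scales already collected? |
|---|---|---|
| First MRI | 2 | No, neither pre nor post |
| VR scenarios, first pass and assigned condition, with ratings | 3 | Collected here |
| Second MRI | 3, after VR | Yes, both |

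A halt at the Visit 2 scan loses both VR scales entirely. A failure at the Visit 3 scan loses neither. The point therefore concerns Visit 2 only.

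**The plan's own power figure.** Inputs from Section 12.0: effect size d = 0.73, pre/post correlation r = 0.6, 20 per group, two-sided alpha 0.05.

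- Residual SD after baseline adjustment: sqrt(1 − r²) = sqrt(1 − 0.36) = 0.8.
- Standardised effect: 0.73/0.8 = 0.9125.
- Noncentrality with arms n1 and n2: 0.9125 × sqrt(n1 × n2/N). At 20 + 20 this is 0.9125 × sqrt(10) = 2.886.
- Power from the noncentral t distribution with N − 3 degrees of freedom (one spent on the covariate): 80.2%.

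The stated 80% reproduces.

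**Value of each child retained.** Same formula, arms as equal as possible. The number retained is an assumption, because the plan does not say how many children Section 11 would halt.

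| Extra children with VR ratings | N | Power | Detectable d at 80% power |
|---|---|---|---|
| 0 | 40 | 80.2% | 0.728 |
| 1 | 41 | 81.2% | 0.719 |
| 2 | 42 | 82.2% | 0.709 |
| 3 | 43 | 83.1% | 0.701 |
| 4 | 44 | 84.0% | 0.692 |

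This is about 1 point of power per child.

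**Upper bound.** If all the planned attrition were due to the scan and recoverable, 40/0.85 = 47.1 to 40/0.80 = 50 children could give VR ratings. Power would be 86.4% at N = 47 and 88.5% at N = 50. This is unlikely, because Section 12.0 attributes attrition to noncompliance or motion and does not mention intolerance of the scanner.

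**If the 95 enrolled are taken literally.** Completers would number 95 × 0.80 × 0.80 = 60.8 to 95 × 0.85 × 0.85 = 68.6, or 61 to 69. Power is then 93.9% at 61 and 94.2% at 62, and 96.2% at 69 and 96.4% at 70. Before rounding, each extra child adds 0.4 points at the lower end and 0.2 at the upper end.

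**The case against.** The strongest reply is that the two sections already fit together. Section 11.0 gives claustrophobia and health events as its examples, so it reads most naturally as a rule about tolerance and safety. A scan spoiled by motion or a fault then falls under Section 7.0, and that child can attend Visit 3. This largely stands. The two rules are not a flat contradiction, and the children clearly affected are only those who cannot tolerate the Visit 2 scan. What remains is that the plan does not draw this line, and that for the claustrophobic child Section 11.0 is explicit.

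Few children should reach that point. MRI contraindications are an exclusion, and so is an investigator's judgement that a child cannot complete the procedures. Visit 1 also includes safety screening and a mock scanner. This stands too: the number could be zero.

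A safety exception would also keep some of these children out, particularly those stopped for a health event. That is right and should remain.

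One cohort able to do every procedure is a legitimate design choice, since both aims concern the same intervention. That is fair, but Section 7.0 already accepts a Visit 3 without a scan.

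A reader might go further and infer three things that the documents do not support:

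- **That the trial is underpowered because of this rule.** The 40 completers are already net of attrition, and the 80% reproduces at that number. Retained children would be a bonus.
- **That the rule biases the comparison between arms.** Randomisation may precede Visit 2, so a child already assigned can be lost. But Section 6.0 keeps the assignment sealed to the research team until within 24 hours of Visit 3, and Visits 1 and 2 are identical in both arms. No difference by arm follows from the text.
- **That the VR analyses exclude children without usable scans.** Section 12.0 states no such restriction. The loss arises from halting the child, not from the models.

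**Conclusion.** The point holds as a cheap improvement of low severity. As written, Section 11.0 stops a child who cannot complete the Visit 2 scan and so discards two primary outcomes that need no MRI, although Section 7.0 already contemplates a Visit 3 without one.

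The benefit is about 1 point of power on each VR scale per child retained at N = 40, and 0.2 to 0.4 points if enrolment of 95 yields 61 to 69 completers. These figures assume the plan's own d = 0.73 and r = 0.6, and that a retained child resembles the others in variance and response. The number of children concerned is unknown and probably small, so the total gain cannot be stated.

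**What to change.** Amend Section 11.0 so that inability to complete a scan ends scanning only, unless there is a safety reason to stop, and the child may continue to the Visit 3 VR procedures. Add a cross-reference to the Visit 3 sentence in Section 7.0 so that both sections give the same rule.

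In Section 12.0, state that both VR scales are analysed as randomised in every child with Visit 3 VR ratings, whatever the scan status, and that only the fMRI outcome is restricted to children with usable scans. No current restriction is being corrected here; the sentence makes explicit how children with VR data only are handled. Report VR completers and fMRI completers separately, since the 40-completer target does not distinguish them.

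The cost is a few lines of protocol wording and no new procedure. The VR and fMRI samples will differ slightly, and a few Visit 3 sessions will yield no fMRI data. If the sponsor prefers to keep halting such children, Section 11.0 should at least say which unsuccessful Visit 2 scans end participation and which do not.
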